5.0	Registration Procedures
6.0	Radiation Therapy
7.0	Drug Therapy
8.0	Other Therapy
9.0	Patient Assessments
10.0	Data Collection
11.0	Statistical Considerations
12.0	Data Safety Monitoring Plan
	References
	Appendix I - Sample Treatment Consent Form Appendix II - Study Parameters Appendix IV - Performance Status Scoring Appendix IV - Staging System Appendix V - Comorbidity Scoring Sheet and Charlson Comorbidity Index (CCI Appendix VI - Cost Effectiveness Analysis Worksheet Appendix VII - FACT-L Worksheet Appendix IX - EQ-5D Worksheet

Schema

Number of patients = 226 (113) per arm)

ELIGIBILITY (see section 3.0 for full criteria)

- Stage II-III or Recurrent (after surgical resection) non-small cell lung cancer (NSCLC) that would benefit from local radiation therapy.
- Zubrod performance status of 2 or greater
- OR Zubrod performance status 0-1 and weight loss > 10% over the last 6 months prior to enrollment OR medically unable to tolerate or refusing standard combined modality therapy
- -Total (aggregate) gross tumor volume ≤ 500 cm³ (500 cc's or 0.5 Liters
- No prior radiotherapy to the chest or neck that would result in overlap of radiation therapy fields
- No chemotherapy within one week prior to study registration/study enrollment except concurrent chemotherapy may be given at the investigator's discretion to patients randomized to the standard arm (arm B, 30-33 fractions)
- Study-specific consent form signed

Eligibility Checklist

not permitted. Subjects must meet all of the inclusion and exclusion criteria to be registered to ment may not begin until a subject is registered.
 (Y) 1. Does the patient have histologically or cytologically documented NSCLC within 9 months of study enrollment?
 (Y) 2. Is TNM Stage II or III or does the patient have recurrent disease after surgical resection?
 What is the patient's TNM stage?
 (N) 3. Has the patient had prior radiotherapy to the chest or neck that would result in overlap of radiation therapy fields?
 (Y) 4. Is the Zubrod performance status 2 or greater?
 What is the patient's performance status (see Appendix III)?
 (Y) If not, does the patient have weight loss > 10% over the last 6 months?
 (Y) If not, is the patient medically unable to tolerate or refusing standard combined modality therapy?
 (Y) 5. Is the total (aggregate) gross tumor volume \leq 500 cm 3 (500 cc's or 0.5 Liters)
 (Y) 6. Is patient ≥ 18 years of age?

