 (N) 7. Has the patient had any chemotherapy within a week prior to study registration/study enrollment?
 (Y/Quit/Never) 8. Does the patient smoke?
 (Y) 9. Were all the required pre-registration/study enrollment evaluations administered as specified in Section 4, including CT with contrast of lung and upper abdomen within 12 weeks of registration/study enrollment?
 (Y/NA) 10. Has the patient agreed to use an effective method of contraception? Women of child-bearing potential and men must agree to use adequate contraception (hormonal or barrier method of birth control; abstinence) prior to study entry, for the duration of study participation, and for 90 days following completion of therapy. Should a woman become pregnant or suspect she is pregnant while participating in this study, she should inform her treating physician immediately.

10a. A female of child-bearing potential is any woman (regardless of sexual orientation, having undergone a tubal ligation, or remaining celibate by choice) who meets the

following criteria:

- * Has not undergone a hysterectomy or bilateral oophorectomy; or * Has not been naturally postmenopausal for at least 12 consecutive months (i.e., has had
- * Has not been naturally postmenopausal for at least 12 consecutive months (i.e., has had menses at any time in the preceding 12 consecutive months).

 (N) 11. If female, is the patient pregnant or lactating?
(Y) 12. Has the patient signed the protocol consent?

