3.0 Patient Selection

3.1 Conditions for patient eligibility

- **3.1.1** All patients must be willing and capable of providing informed consent to participate in the protocol.
- 3.1.2 Patients must have appropriate staging studies identifying them as AJCC stage II or III non-small cell lung cancer, (according to AJCC Staging, 6th edition; see appendix III), or recurrent non-small cell lung cancer. Histologic confirmation of cancer will be required by biopsy or cytology within 9 months of study enrollment.
- **3.1.3** Patients must have the potential for benefit from local therapy (at the discretion of the investigator).
- **3.1.4** The patient's Zubrod performance status must be 2 or greater, OR patients with Zubrod performance status 0-1 and weight loss >10% over the last 6 months prior to enrollment,

OR patients determined to be medically unfit or refusing combined modality therapy are considered eligible.

- **3.1.5** Age ≥ 18.
- **3.1.6** Patients must have measurable or evaluable disease by RECIST 9.3 criteria.
- **3.1.7** Women of childbearing potential and male participants must agree to use an effective method of contraception.

Women of child-bearing potential and men must agree to use adequate contraception (hormonal or barrier method of birth control; abstinence) prior to study entry, for the duration of study participation, and for 90 days following completion of therapy. Should a woman become pregnant or suspect she is pregnant while participating in this study, she should inform her treating physician immediately.

A female of child-bearing potential is any woman (regardless of sexual orientation, having undergone a tubal ligation, or remaining celibate by choice) who meets the following criteria:

- * Has not undergone a hysterectomy or bilateral oophorectomy; or
- * Has not been naturally postmenopausal for at least 12 consecutive months (i.e., has had menses at any time in the preceding 12 consecutive months).
- **3.1.8** Patients must sign study specific informed consent prior to study enrollment.
- **3.1.9** While patients randomized to the standard arm (Arm B, 30-33 fractions) may receive concurrent chemotherapy with carboplatin/taxol at their treating physician's discretion, patients enrolled to the experimental arm (Arm A, 15 fractions) cannot be treated with concurrent chemoradiation and must not have plans for concurrent chemoradiation therapy. Sequential chemotherapy (prior to or after radiotherapy) is allowed for either arm.

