3.2 Conditions for patient ineligibility

- **3.2.1** Total (aggregate) gross tumor volume > 500 cm³ (500 cc's or 0.5 Liters)
- **3.2.2** Prior radiotherapy to the region of the study cancer that would result in direct overlap of radiation therapy fields.
- **3.2.3** Chemotherapy given within one week of study registration/enrollment except concurrent chemotherapy may to be given at the investigator's discretion to patients randomized to the standard arm (arm B, 30-33 fractions).
- **3.2.4** Pregnant or lactating women, as treatment involves unforeseeable risks to the embryo or fetus.

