5.2 Registration

Prior to registration/study enrollment, participating investigators and institutions should review the eligibility checklist and confirm eligibility. Patients can be registered only after eligibility

criteria are met. To register a patient, the site should fax the Enrollment Form to the Project Manager ([contact]. A unique, participant ID number will then be assigned.

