11.5 Analysis Plans

All eligible patients who are randomized to the study will be included in the comparison of treatment arms, regardless of treatment compliance (intent-to-treat analysis).

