12.3 Registration/Randomization Procedure

All subjects must be registered with the Radiation Oncology before enrollment to study. Prior to registration, eligibility criteria must be confirmed with the Radiation Oncology Study Coordinator. To register a subject, call [name] Monday through Friday, 9:00AM-5:00PM

Each newly consented subject should be numbered using the schema provided above. Upon registration, the registrar will assign the additional registration/randomization code according to the numbering schema outlined above, which should then be entered as the patient study id in Velos upon updating the status to enrolled.

The numbering schema should clearly identify the site number; the sequential number of the subject enrolled as well as the status of the subjects enrolled so that the number of subjects consented versus the number of subjects actually enrolled may be easily identified.

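### Section 11.5 calls an eligible-only comparison intent-to-treat while 3.1.9 sets an eligibility condition for Arm A alone, which leaves a narrow, avoidable opening for arm-dependent exclusion

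*Combined protocol and SAP*

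**What the plan says.** Section 11.5 defines the set for comparing the arms: "All eligible patients who are randomized to the study will be included in the comparison of treatment arms, regardless of treatment compliance (intent-to-treat analysis". Two conditions are joined there, eligible and randomized. The compliance clause protects patients who depart from treatment; it does not speak to patients judged ineligible.

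Section 3.1.9, under the conditions for eligibility, says that Arm A patients "cannot be treated with concurrent chemoradiation and must not have plans for concurrent chemoradiation therapy", and lets Arm B patients receive concurrent chemotherapy. Section 3.2.3, under the conditions for ineligibility, excludes recent chemotherapy but adds that "concurrent chemotherapy may to be given at the investigator's discretion to patients randomized to the standard arm". Section 7.0 repeats the arm-specific chemotherapy rule as a treatment rule.

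Eligibility is to be settled before entry. The Eligibility Checklist states: "Subjects must meet all of the inclusion and exclusion criteria to be registered". Section 5.2 states "Patients can be registered only after eligibility" criteria are met. Section 12.3 adds that before registration "eligibility criteria must be confirmed with the Radiation Oncology Study Coordinator". The only chemotherapy question on the checklist is item 7: "Has the patient had any chemotherapy within a week prior to study registration/study enrollment".

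Section 11.2 raises accrual from 226 to 238 to allow for up to 5% ineligibility or lack of data. Section 9.6.2 measures survival from enrollment and follows all patients for it.

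**The concern.** Leaving out ineligible patients is usually tolerable when every criterion is fixed before allocation and is the same in both arms. Section 3.1.9 does not meet that test, because it names the arm. A condition on Arm A patients alone cannot be fully applied until the arm is known, so two patients with the same baseline facts could be eligible in Arm B and ineligible in Arm A.

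The checklist does not close the gap, since item 7 asks about past chemotherapy and not about plans. The case left open is an Arm A patient who is found after randomization to have had a plan for concurrent chemotherapy. That patient could be ruled ineligible and dropped, while the matching Arm B patient stays. Such a removal would come after randomization, in a comparison where treatment is known, and would fall on one arm only. It could bias overall survival, the primary endpoint, in either direction.

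The route is limited by how patients enter. Under 3.1.4 "patients determined to be medically unfit or refusing combined modality therapy are considered eligible", and patients who enter that way should have no such plan. Those who enter on performance status or weight loss might. Section 1.4 reports that oncologists use concurrent chemotherapy case by case in this population.

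**Working it through.** **1. The plan's own figures (11.2).** Inputs: 1-year survival 45% and 60%, two-sided 0.05, 80% power, log-rank test, 2 years' uniform accrual plus 1 year of follow-up.

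- Hazards: −ln 0.45 = 0.799 and −ln 0.60 = 0.511; hazard ratio 0.640.
- Events (Schoenfeld): 4 × (1.960 + 0.842)² / (ln 0.640)² gives 158.
- Event probability: 1 − [exp(−λ) − exp(−3λ)] / (2λ) = 0.775 (control) and 0.624 (experimental); mean 0.700.
- N = 158 / 0.700 = 226 after rounding. With the 5% allowance, 226 / 0.95 = 238.

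Both stated figures reproduce. The allowance is 238 − 226 = 12 patients, 6 per arm.

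**2. What the texts settle.**

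| Case | Governing text | Result |
|---|---|---|
| Either arm, fails a common criterion before entry | Checklist, 5.2, 12.3 | Not registered |
| Arm A, receives concurrent chemotherapy | 7.0 with the compliance clause of 11.5 | Most naturally kept as non-compliant, although 3.1.9 also lists it under eligibility |
| Arm A, plan for concurrent chemotherapy found after randomization | 3.1.9 with the word eligible in 11.5 | Not settled |
| Arm B, same plan | 3.1.9 permits it | Kept |

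**3. Size of the open case.** The documents give neither how many such patients there would be nor their prognosis, so both are assumed. Let a share q of patients have hazard r times the rest:

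S(t) = (1 − q) exp(−λt) + q exp(−rλt), with λ chosen so that S(1) = 0.45.

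There is no true treatment effect, 119 patients per arm, and the 11.2 timing. The share q is removed from Arm A only: q = 0.025 (about 3 of 119) or 0.05 (about 6 of 119, Arm A's whole share of the allowance). The large-sample Cox hazard ratio and the log-rank drift z come from numerical integration. Total two-sided error = Φ(−1.96 − z) + Φ(z − 1.96).

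Example, q = 0.05 and r = 0.3: λ = 0.838 and z = 0.382, so the error is Φ(−2.342) + Φ(−1.578) = 0.010 + 0.057 = 0.067.

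| Removed from Arm A | r | Null HR (A vs B) | Total two-sided error |
|---|---|---|---|
| 3 | 0.3 | 1.03 | 5.4% |
| 3 | 0.5 | 1.02 | 5.2% |
| 3 | 1 | 1.00 | 5.0% |
| 3 | 2 | 0.98 (0.985) | 5.1% |
| 3 | 3.33 | 0.98 (0.978) | 5.3% |
| 6 | 0.3 | 1.06 | 6.7% |
| 6 | 0.5 | 1.04 | 5.6% |
| 6 | 1 | 1.00 | 5.0% |
| 6 | 2 | 0.97 | 5.5% |
| 6 | 3.33 | 0.96 | 6.1% |

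The excess falls on one side. With 6 removed, the nominal 2.5% becomes 5.7% favouring B (r = 0.3) or 4.9% favouring A (r = 3.33). At the planned ratio of 0.64, the same two cases give HR 0.68 with power 70%, or HR 0.61 with power 87%, against 79–80% with everyone kept. The apparent gain in power is bias, not information.

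A simulation with another selection rule (removals drawn from the shorter- or longer-surviving half of Arm A) gives HR about 0.95 or 1.05 and total error about 6% for 6 removals.

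**4. Cost of keeping everyone.** On the same timing and with exponential survival, 238 patients give 238 × 0.700 = 166.5 events and 82.2% power, against 158.1 events and 80.2% if 12 are left out.

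**The case against.** The strongest reply is that the documents nearly close the opening themselves. All criteria must be met and confirmed before registration, so the eligible randomized patients are in effect everyone properly registered. Section 12.5 treats departures from the protocol, including single-subject eligibility exceptions, as matters to approve or report, not as grounds for removal from analysis. Section 9.5 continues follow-up after treatment stops. The open case also needs a chain of events: a plan existed, the patient was registered anyway, the plan came to light, and it was ruled a matter of eligibility, not compliance. Section 10.0 makes eligibility data due within 2 weeks of enrollment but names no item on planned chemotherapy, so no stated route leads to such a removal.

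Most of this stands, and it is why the point is small. It does not dispose of it. Those sections govern registration, deviations and follow-up; none says who enters the analysis. Section 11.5 does, and it uses the word eligible without tying it to facts fixed before allocation. Section 11.2 also budgets for ineligibility, which fits dropping such patients.

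A reader might also take 3.2.3 as a second source of arm-dependent exclusion. The documents hardly support that. The schema and checklist item 7 limit the exclusion to chemotherapy before registration, when nobody is on an arm, so the Arm B exception then treats no one differently. Only the looser wording of 3.2.3, within one week of registration without saying before, could reach further. That is a secondary inconsistency to reconcile.

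**Conclusion.** The point holds in a narrow form. The intent-to-treat label does not match an eligible-only set, and one eligibility condition binds Arm A alone, so an arm-dependent exclusion after randomization is neither ordered nor ruled out.

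A reader might infer that the plan directs such exclusions, that Arm A patients given concurrent chemotherapy will be dropped, or that the survival comparison is biased in a known direction. None of these is supported: no passage orders a removal, the compliance clause most naturally keeps treated patients, and nothing is said about the prognosis of anyone who might be removed.

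Size and direction are unknown, and the effect is nil if those removed have average prognosis. With 3 to 6 of 119 removed from Arm A, the null hazard ratio lies between 1.06 and 0.96, and total two-sided error reaches about 5.3–6.7% at the assumed extremes (r = 0.3 or 3.33). Six removals is already an upper case, since it gives this one route Arm A's whole share of an allowance meant for all ineligibility and missing data. The figures ignore the interim look and use the 2-year accrual of 11.2, although 11.3 projects 60 months. This is a cheap improvement worth making, not a defect that undermines the trial.

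**What to change.** - In 11.5, state that all randomized patients are analysed for overall survival in the arm assigned, regardless of eligibility or treatment received, with patients lost to follow-up censored at last contact.
- Make any eligible-only analysis a sensitivity analysis that uses only criteria fixed before randomization and identical in both arms.
- State that a breach of the Arm A chemotherapy rule counts as non-compliance for the analysis.
- Reconcile 3.1.9, 3.2.3, 7.0, the schema and the checklist so that no eligibility criterion depends on the assigned arm and the time window reads the same throughout. This need not change any chemotherapy rule.

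The first change alone removes the problem from the primary analysis; the others keep the texts consistent with it. The cost is wording only, and the sample size stays as planned. The downside is that a few ineligible patients may slightly dilute the effect.

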11.5.1 Overall Survival

Overall survival time will be estimated using the Kaplan-Meier approach. The stratified log-rank test will be used to test for a statistically significant difference in survival distributions. The null and alternative hypotheses are H_0 : $S_1(t) < S_2(t)$ vs. H_A : $S_1(t) \ge S_2(t)$, where $S_i(t)$ is the distribution of overall survival times for patients in arm i.

The Cox proportional hazard regression model will be used to determine hazard ratios and 95% confidence intervals for the treatment difference in overall survival. Unadjusted ratios and ratios adjusted for stratification variables and other covariates of interest will be computed.

11.5.2 Quality of Life (Functional Assessment of Cancer Therapy-L):

Patient-reported functional status will be assessed with the lung cancer subscales of the Functional Assessment of Cancer Therapy-Lung (FACT-L). The FACT-L is a 36-item questionnaire that uses 5-point Likert-type response choices (0 = not at all; 1 = a little bit; 2 = somewhat; 3 = quite a bit; 4 = very much). It will take less than 10 minutes to complete the questionnaire. The Trial Outcome Indices (TOI) also will be utilized to measure the summed functional well-being, physical well-being, and the additional concerns (lung symptom module) subscales of the FACT-L. A 5-point deterioration in the FACT-L TOI between pre-treatment and at year 1 will be considered clinically significant. The patient-reported endpoint will be a difference in the deterioration from the pre-induction FACT-L TOI score to the score at 6-month post-treatment. This score measures functional status and a difference of 5 FACT-L TOI points will be considered clinically significant.[33]

The first analysis of change in QOL from baseline to 6 months will only be performed on patients who are still alive at 6 months. Changes in QOL will be also analyzed using all available data at baseline, 6, and 12 months with generalized estimating equations (GEE). We will also compare the percentage of patients in each arm with an effect size for the change in FACT-L TOI scores between pre-induction and 6 months of < .2; this will allow us to compare the percentage of patients in each arm whose functional status remains more similar to baseline levels.

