Specifically, the experimental arm dose for this trial is based on a dose escalation trial at University of Texas Southwestern evaluating the maximum tolerated dose of hypofractionated IGRT in this patient population. Doses were escalated from 3 Gy per fraction (total dose 45 Gy) to 4.0 Gy per fraction (total dose 60 Gy) and evaluation for treatment related toxicity was being performed. Critical structure dose constraints will be expressed as organ dose-volume limits, with limits formulated with the approval of the study investigators using known tolerance data, radiobiological conversion models, and norms used in current practice at academic centers [27]. The trial design called for treating many patients per dose level, akin to a phase II trial, so as to collect outcome data on enough patients to simultaneously appreciate toxicity and efficacy in order to optimize dosing. The maximum tolerated dose (MTD) was never reached on this protocol up to 60 Gy in 15 fractions for effectively the same population treated on this protocol. 50 Gy, 55 Gy or 60 Gy in 15 fractions was delivered using image guided radiation therapy. Patents with tumor volumes larger than 500 cc were excluded. 18, 23 and 21 individuals were enrolled at each dose level respectively. The median follow-up is 195 days (range 26-927 days). Median follow-up is 452 days if patient deaths are censored in a population that succumbs commonly to non-cancer or treatment related causes. Of

the 52 patients enrolled, only 4 patients experienced grade 3 or higher treatment-related toxicity spread indiscriminantly among the tested dose levels. Long term tumor control from this trial is still being collected. Since previous trials described above show improving control and survival with radiation dose intensification and since the MTD was not reached, we have chosen the 60 arm to be the experimental arm of this protocol.

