9.7 Comorbidity Data and Rating

The Charlson Comorbidity index will be used to assess pretreatment comorbidity status (see Appendix V).

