11.0 Statistical Considerations

11.1 Study Endpoints

11.1.1 Primary Endpoint: Overall survival (Failure: death from any cause)

11.1.2 Secondary endpoints:

11.1.2.1 Quality of Life (QOL) as measured by the Functional Assessment of Cancer Therapy Lung subscale (FACT-L)

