11.1.2.4 Toxicity: Grade 3-5 adverse events as graded by CTCAE v 4.0

11.2 Sample Size Determination

The sample size calculation is based on the primary endpoint, overall survival at 1 year, and the assumption that patients are randomized until the end of accrual. The sample size is calculated with the 2-sided significance level of 0.05 and 80% statistical power using a 2-sample log rank test. We assume that the overall survival function follows an exponential distribution for each arm. Accrual to the study is assumed to be uniformly distributed. The null hypothesis is that the there are no difference in 1-year survival rates between two arms. We assume that the patients will be accrued for 2 years with a 1-year follow-up. We hypothesize that the patients randomly assigned to the control arm and experimental arm have a 1-year survival rate of 45% (hazard rate [λc]) of 0.799) and 60% (hazard rate [λe]) of 0.511), respectively, which is translated to the hazard ratio of $\lambda e/\lambda c = 0.640$. One interim analysis and a final analysis are planned for early stopping for efficacy. The efficacy testing is based on the Lan-DeMets spending function, which resembles the O'Brien-Fleming boundary. The total sample size of 226 patients (113 in the control arm and 113 in the experimental arm) will be accrued to achieve the desired 80% statistical power and 2-sided significance level of 0.05. Guarding against ineligibility or lack-ofdata rate of up to 5%, the final targeted accrual for this study will be 238 patients (119 per arm). Sample size was estimated using the sample size software EaST version 5.

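### The primary survival comparison adjusts only for performance status and stage; one prespecified Cox model adding Charlson score and age may gain power without extra patients

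*Combined protocol and SAP*

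**What the plan says.** All references are to the combined protocol and SAP.

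- **Deciding test (11.5.1):** "The stratified log-rank test will be used to test for a statistically significant difference in survival distributions". Section 11.4 names two stratifying variables, Zubrod performance status (2 vs >2) and stage (II vs III).
- **Effect estimates (11.5.1):** a Cox model with 95% confidence intervals, and then "Unadjusted ratios and ratios adjusted for stratification variables and other covariates of interest will be computed". The further covariates are not listed, and no ratio is designated as the primary estimate.
- **Comorbidity (9.7):** "The Charlson Comorbidity index will be used to assess pretreatment comorbidity status". Appendix II places the index within the 12 weeks before registration, and Appendix V gives the scoring sheet. Section 11 does not mention it.
- **Age:** confirmed at eligibility (3.1.5) and fixed at entry. It also has no named role in section 11.
- **Design basis (11.2):** "The sample size is calculated with the 2-sided significance level of 0.05 and 80% statistical power using a 2-sample log rank test". The two arms "have a 1-year survival rate of 45% (hazard rate [λc]) of 0.799) and 60% (hazard rate [λe]) of 0.511), respectively".

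**The concern.** Adjusting for a strong baseline predictor usually makes a survival comparison more powerful and keeps chance imbalance in that predictor out of the answer. The plan itself suggests that patients differ in risk. Section 1.1 describes poor-performance patients as a mixed group in which comorbidity and age play a part. Section 1.2 describes "a population that succumbs commonly to non-cancer or treatment related causes". That remark also covers treatment-related deaths and does not say that the Charlson score predicts death, so it motivates the question without answering it.

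Two things are at stake. One is power that could be had from data already being collected. The other is the effect estimate. Treatment is visible (15 vs 30-33 fractions), the covariates are unnamed, and several hazard ratios are promised with none in charge. Nothing in the text stops the covariates being chosen once results are known.

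**Working it through.** **1. The plan's own figure.** Inputs from 11.2: 1-year survival 45% and 60%, two-sided 0.05, 80% power, exponential survival, 2 years of uniform accrual and 1 year of follow-up.

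- Hazards: −ln 0.45 = 0.7985 and −ln 0.60 = 0.5108. Ratio 0.6397 (stated 0.640).
- Events (Schoenfeld): 4(1.960 + 0.842)² / (ln 0.6397)² = 157.3, rounded up to 158.
- Event probability per arm: 1 − (e^−λ − e^−3λ)/(2λ), which is 0.775 for control and 0.624 for experimental. Mean 0.6997.
- N = 158 / 0.6997 = 225.8 (stated 226). Power at the 158.1 events expected from 226 patients is 80.2%. An assumed O'Brien-Fleming inflation of 1.008 would give 227.6.
- 226 / 0.95 = 237.9 (stated 238).

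The stated design reproduces.

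**2. Which baseline data enter which analysis.**

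| Variable | Known before treatment on all? | Primary test | Cox ratios |
|---|---|---|---|
| Zubrod status, stage | Yes | Yes, as strata | Yes |
| Charlson index | Scheduled (9.7, Appendix II) | No | Not named |
| Age | Yes | No | Not named |
| Weight loss >10% | Checklist asks only if Zubrod is below 2 | No | Not named |
| Gross tumor volume | Checklist asks only yes/no against 500 cc | No | Not named |

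**3. What adjustment would add.** The documents give no prognostic strength for any covariate, so a range was simulated: 226 patients, accrual and follow-up as in 11.2, marginal 1-year survival held at 45% and 60%, and 10,000 trials per row (Monte Carlo error about 0.4 points). Assumed strata: 30% with Zubrod >2 (hazard ratio 1.5) and 80% stage III (hazard ratio 1.3). One standard-normal covariate stands for Charlson and age combined. There was no interim look.

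| Assumed HR per SD beyond strata | Stratified log-rank | Stratified Cox + covariate | Difference (points) |
|---|---|---|---|
| 1.00 | 79.9% | 79.6% | −0.4 |
| 1.11 | 79.9% | 79.8% | −0.1 |
| 1.22 | 79.9% | 81.2% | +1.2 |
| 1.35 | 78.8% | 81.7% | +2.9 |
| 1.49 | 78.4% | 83.2% | +4.8 |
| 1.65 | 76.1% | 83.8% | +7.7 |

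Differences were taken before rounding. Type I error at 1.35 per SD was 5.2% for the log-rank and 5.3% for the Cox test. In a separate unstratified run (4,000 trials) with four covariates that carried no information, power was 81.6% unadjusted and 81.2% adjusted, so several useless terms also cost under half a point.

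**4. Does the fall in the log-rank column show that 80% is wrong?** No. Those rows fix survival at 1 year only, so the arm-level curves bend away from the exponential shape that 11.2 assumes. When the arm curves were kept exponential at 45% and 60% (2,500 trials), unadjusted power stayed at 79-81% even with large differences in risk between patients.

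**5. The estimand.** The conditional hazard ratio in the step 3 simulations ran from 0.635 down to 0.612, against a marginal 0.64.

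**The case against.** A log-rank test stratified by the randomization factors is a standard primary analysis, it uses two prognostic variables, and it meets the plan's own power target. All of that stands. A reader might infer that the comparison ignores baseline prognosis altogether. It does not, because performance status and stage are in the test and adjusted ratios are planned.

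A reader might also infer that the trial is underpowered, or that several points of power are certainly being lost. The documents support neither. Exponential curves at arm level do not exclude differences between patients, and with a weak covariate the gain is nil. A gain of about 13 points (74.8% to 88.1%) appears only at a hazard ratio near 2.0 per SD and against an unstratified test, which is not the test planned here. The simulations are also favorable to adjustment, since the covariate enters in its correct form.

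It is tempting to add weight loss and tumor volume. Neither is shown to be available at baseline on everyone. The checklist does not ask about weight loss once Zubrod is 2 or more. Section 6.1 allows simulation before registration without requiring it, so tumor contours could be drawn after the arm is known.

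Finally, changing the primary test after enrollment has begun (11.5.9 refers to the first 44 patients) is not free. The interim boundary and the conditional-power rule must follow the new test. This objection limits how and when the change is made. It does not remove the need to name the covariates and one primary estimate.

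**Conclusion.** The point holds as an improvement and does not show an error in the design. The test that decides the trial adjusts only for performance status and stage, two further baseline variables have no stated use, and the adjusted estimate is left open. The gain is about 0 points at a hazard ratio of 1.1 per SD, +1 at 1.22, +3 at 1.35, +5 at 1.49 and +8 at 1.65. The downside is under half a point and type I error stays near 5%. These figures rest on assumed prognostic strength beyond the strata, assumed stratum sizes and effects, and a fixed design without the interim. A gain of several points needs roughly 1.35 per SD or more, which the documents neither give nor rule out. Prespecifying the covariates and one primary estimate is worthwhile whatever the gain.

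**What to change.** Before the interim look, and without access to comparative data, amend 11.5.1 as follows.

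- Specify a Cox model stratified by the randomization strata, with treatment, Charlson score and age. State the form of each covariate and the rule for missing values.
- Make its treatment hazard ratio and 95% CI the single primary estimate. Preferably make its treatment test the primary test, under the same Lan-DeMets boundary. If the sponsor keeps the log-rank as the test, this model should still supply the one designated estimate.
- Report the planned stratified log-rank and the unadjusted ratio as supportive, and replace the open-ended covariate wording with the named list.
- Add weight loss or tumor volume only if a pre-randomization value is captured on all patients.

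The cost is SAP text and modest programming, with no change to 226 or 238 patients. The section 10 submission table has no separate line for the Charlson sheet, so confirm that it reaches the trial database. The hazard ratio becomes conditional on the covariates, and the interim and final analyses must use the same test.
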